### **8.2.3 Radiographic Soft Tissue Progression per RECIST 1.1 Criteria (at least 1 of the following):**

Twenty percent increase in the sum of appropriate diameters of target measurable lesions over smallest sum observed (over baseline if no decrease during therapy) using the same techniques as baseline, as well as an absolute increase of at least 0.5 cm.

Unequivocal progression of non-measurable disease in the opinion of the treating physician (an explanation must be provided).

Appearance of any new lesion/site.

Lesions that appear to increase in size due to presence of necrotic tissue will not be considered to have progressed.

Appearance of new pleural effusions does not constitute unequivocal progression unless cytologically proven of neoplastic origin, since some effusions are a toxicity related to therapy or other medical conditions.

Increase in the size of an existing effusion does not constitute unequivocal progression, since the fluid status of the subject could alter the size of the effusion.

### **8.2.4 Symptomatic Deterioration**

Global deterioration of health status requiring discontinuation of treatment without objective evidence of progression. Efforts should be made to obtain objective evidence of progression after discontinuation.

### **8.3 Performance Status**

Subjects will be graded according to the ECOG Performance Status Scale. Please see Study Procedures Manual (SPM).

### **8.4 Two Year PSA Progression-Free Survival**

From date of randomization to first occurrence of PSA progression, symptomatic deterioration, or death due to any cause. Subjects without progression are censored at last date of contact.

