12. For late induction subjects, Cycle 1 Day 1 will occur after screening and upon completion of eligibility. C1D1 lab testing need not be repeated if completed within 7 days of starting protocol therapy. For early induction subjects, C1D1 occurs prior to screening; documentation of initiation of ADT (C1D1) should occur after review of the subject chart and completion of eligibility.
13. For maintenance Cycles 14-17, subjects will continue to be followed every 12 weeks for alkaline phosphatase, PSA values and AE/concomitant medication updates, initiation of new anti-cancer therapy and occurrence of secondary malignancies. This information may be obtained via local treating physician medical records.
14. The end of treatment/follow up column will be utilized for subjects that come off protocol therapy (both Arm A and Arm B) for toxicity or progression. If this occurs, subjects should have an end of treatment visit 30 days ( $\pm$  7 days) after discontinuation of protocol therapy. Subjects will then continue to be followed every 3 months for a total of 2 years from the date of randomization. If a subject withdraws consent, he is deemed "off study" and will NOT be followed further. Follow up may occur via phone call, email or other communication. If available by medical record review, alk phos, PSA, AE/concomitant medication should be obtained.

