### 7.10 End of Treatment (EOT) and Follow Up

The end of treatment/follow up column will be utilized for subjects that come off protocol therapy (radium-223 dichloride if randomized to that Arm and ADT) for toxicity or progression. If this occurs, subjects should have an end of treatment visit 30 days ( $\pm$  7 days) after discontinuation of protocol therapy. Subjects will then continue to be followed every 3 months for a total of 2 years from the date of randomization. Follow up may occur via phone call, email or other communication. If available by medical record review, alk phos, PSA, AE/concomitant medication should be obtained. Testing to be done at the EOT visit:

- Circulating tumor cell's (CTCs)
- Serum bone turnover markers
- Banking Samples: serum, plasma
- Alkaline phosphatase
- PSA

If a subject withdraws consent, he is deemed **“off study”**. “Off study” subjects will not be followed further.

A subject will be discontinued from the protocol specified therapy under the following circumstances:

- If there is evidence of radiologic disease progression or symptomatic deterioration despite castration range serum testosterone level ( $< 50$  ng/dL). Such subjects can go on to other treatment outside the study as clinically indicated including continuation or initiation of radium-223 dichloride therapy. They will remain on follow-up portion of the study for a total of 2 years from the date of randomization.
- If there is development of castration-resistant prostate cancer by PSA criteria in conjunction with castration range serum testosterone level ( $< 50$  ng/dL). Castration resistant prostate cancer is defined as two consecutive increases in PSA over the nadir PSA, at least two weeks apart **AND** an absolute increase of at least 2 ng/mL from the nadir PSA (or from baseline PSA if there was no drop in PSA after starting treatment). Discontinuation of bicalutamide may be attempted at the investigator's discretion in such cases and would NOT constitute going “off treatment”. If no response to bicalutamide discontinuation, such subjects may receive other treatment outside the study as clinically indicated including continuation or initiation of radium-223 dichloride therapy. They will remain on follow-up portion of the study for a total of 2 years from the date of randomization.

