- If a subject requests to discontinue protocol specified therapy for any reason at any time. Subjects can stop protocol therapy at any time (off treatment). Such subjects may receive other treatment outside the study as clinically indicated including continuation or initiation of radium-223 dichloride therapy. However, subjects will continue to be followed for survival status and for secondary malignancies as reported by subjects every 3 months for a total of 2 years from the date of randomization unless they withdraw consent (if consent withdrawn, they will be deemed to be off study).

- If androgen deprivation therapy exhibits unacceptable toxicity. Such subjects may receive other treatment outside the study as clinically indicated including continuation or initiation of radium-223 dichloride therapy. **NOTE:** Subjects off bicalutamide or radium-223 dichloride for toxicity but continuing on LHRH agonist/antagonist or have had surgical castration remain on protocol specified therapy.
- If **ALL** protocol specified therapy is interrupted for > 28 days due to a treatment related adverse event. **NOTE:** A delay of up to 7 days in administering the scheduled dose of LHRH agonist or LHRH antagonist is allowed. A delay of up to 56 days in administering the scheduled dose of radium-223 dichloride is allowed if it is due to inadequate hematologic parameters or drug supply issues.

All reasons for protocol therapy discontinuation must be clearly documented.

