## 8.2 Progression Criteria

**8.2.1 PSA progression** is defined by two consecutive increases in PSA over the nadir PSA, at least two weeks apart AND an absolute increase of at least 2 ng/mL from the nadir PSA (or from baseline PSA if there was no drop in PSA after starting treatment).

**8.2.2 Radiographic Skeletal progression on bone scan** is defined as 2 or more new lesions on radionuclide bone scans (PCWG2 criteria). Should two or more new bone lesions be evident at the first imaging assessment (at end of protocol specified therapy), two or more additional new lesions must be evident on a confirmatory assessment at least 6 weeks later.

A bone scan may be ordered at the discretion of the treating physician within the first 7 months of protocol treatment for symptoms e.g. bone pain. If new bone lesions appear in the absence of a rising PSA within the first 7 months of protocol treatment, the site investigator at the institution must consult the sponsor-investigator (via the HCRN Project Manager) to discuss the possibility of tumor flare.

For bone disease documented on bone scan only, increased uptake does not constitute unequivocal progression. However, increase in the soft tissue component of a lesion as measured by CT or MRI would constitute progression.

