### **8.8 Radiographic Progression-Free Survival**

Time to Radiographic progression or death, whichever occurs first, will be calculated for each subject. Subjects who do not have radiographic progression or death upon follow-up will be censored at their last radiographic assessment.

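### PSA progression-free survival is censored at last contact rather than last PSA, so any follow-up time without PSA counts as PSA-progression-free and raises the 2-year estimate

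*Combined protocol and SAP*

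**What the plan says.** Section 8.4 counts PSA-PFS "From date of randomization to first occurrence of PSA progression, symptomatic deterioration, or death due to any cause". It then sets the censoring rule: "Subjects without progression are censored at last date of contact". Section 12.7 plans a 2-year Kaplan-Meier proportion per arm with a 90% confidence interval in the ITT population, and gives no other censoring rule for this endpoint.

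Under Section 8.2.1, PSA progression "is defined by two consecutive increases in PSA over the nadir PSA, at least two weeks apart", together with an absolute rise of at least 2 ng/mL.

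For subjects who have come off therapy, Section 7.10 says "Follow up may occur via phone call, email or other communication". It and calendar footnote 14 add "If available by medical record review, alk phos, PSA, AE/concomitant medication should be obtained". Of subjects stopped for radiographic progression or for castration resistance by PSA, Section 7.10 says "They will remain on follow-up portion of the study for a total of 2 years from the date of randomization". Of those who ask to stop, it says "subjects will continue to be followed for survival status and for secondary malignancies as reported by subjects every 3 months"; PSA is not mentioned.

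Other places point the other way. Calendar footnote 4 has PSA followed monthly for one year from randomization and 12-weekly for the next, exempting only those who withdraw consent. The calendar marks PSA in the end-of-treatment and follow-up column.

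For the primary endpoint, Section 8.8 says event-free subjects "will be censored at their last radiographic assessment". Section 12.6 agrees.

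**The concern.** A phone call can establish that a subject is alive. It cannot show two rising PSA values. Under Section 8.4, a subject who is telephoned but has no PSA drawn stays in the risk set until the last call, and during that time the PSA component of the endpoint cannot occur. The Kaplan-Meier denominator is then too large for the events that can be observed, and the 2-year proportion is pushed up.

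The exposed subjects are those who leave therapy without a PSA-PFS event: for radiographic progression (which ends therapy under Section 7.10 but is not an event under Section 8.4), for toxicity of androgen deprivation therapy, at their own request, or after prolonged interruption of all therapy. At stake are the two per-arm 2-year proportions named in Section 2.2.2 and, if exposure differs by arm, the log-rank comparison of this secondary endpoint.

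**Working it through.** **The plan's own figure.** The documents state no expected PSA-PFS value, so there is none to reproduce. The one design calculation, 140 rPFS events, does reproduce. With hazard ratio 12/19, 1:2 allocation, one-sided 0.10 and 90% power, (1.2816 + 1.2816)² / [(1/3)(2/3)(ln(12/19))²] = 140.0. It has no bearing on this point.

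**Closed-form illustration.**

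Inputs:
- True 2-year PSA-PFS: 33% (exponential, median 15 months) or 25%. Both are assumed.
- Death rate: median 44 months, the ADT-alone overall survival cited in Section 1.5, used for illustration. μ = ln 2/44 = 0.01575 per month.
- A share p of subjects is assigned a time L, uniform over months 7 to 24, after which contact continues to month 24 without PSA. p = 10, 20 or 30%, assumed. Subjects with an event before L are unaffected.
- Deaths after L are still recorded as events.

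Let λ be the total event rate and S(24) = exp(−24λ). A subject in the share p is recorded as event-free at month 24 if there is no event by L and no death from L to 24. The average probability is

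Q = exp(−24μ) × [exp(−7k) − exp(−24k)] / (17k), with k = λ − μ.

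With contact complete to month 24, the reported proportion is S(24) + p × [Q − S(24)].

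- True 33%: λ = ln 2/15 = 0.04621, k = 0.03046, S(24) = 0.330, Q = 0.6852 × 0.6307 = 0.432. The excess is p × 0.102.
- True 25%: λ = ln 4/24 = 0.05776, k = 0.04201, S(24) = 0.250, Q = 0.6852 × 0.5326 = 0.365. The excess is p × 0.115.

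| p | True 33.0% reported as | True 25.0% reported as |
|---|---|---|
| 10% | 34.0% | 26.1% |
| 20% | 35.0% | 27.3% |
| 30% | 36.1% | 28.4% |

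If deaths after L were missed too, the 33% row would read 34.7, 36.4 and 38.1%. That overstates the problem, because Section 8.4 counts deaths and phone contact finds them.

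**Simulation on the protocol's PSA schedule.** This used 400,000 subjects per scenario, PSA-progression medians of 12 or 19 months (borrowed from the rPFS assumptions in Section 12.1), the same death rate, and subjects leaving therapy at 10% per year, all then phone-only.

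| PSA median | True 2-year PSA-PFS | Censor at last contact | Censor at last PSA, later deaths not counted | Censor survivors at last PSA, later deaths counted |
|---|---|---|---|---|
| 12 months | 17.2% | 21.2% | 17.1% | 16.5% |
| 19 months | 28.7% | 32.1% | 28.6% | 27.6% |

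Across 5 to 40% per year leaving and 50 to 100% of them phone-only, last-contact censoring overstated by about 1 to 14 points. With nobody phone-only, the bias was zero.

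**When leaving is related to PSA risk** (12-month median, 10% per year, all phone-only, later deaths not counted under the last-PSA rule):
- PSA hazard doubles after leaving: true 15.6%, last contact 21.1%, last PSA 17.1%.
- PSA hazard halves: true 18.4%, last contact 21.1%, last PSA 16.9%.

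In both cases last-PSA censoring is closer to the truth, but not exact.

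**The case against.** The strongest reply is that the protocol does require PSA after therapy: footnote 4 and the follow-up column of the calendar run to 2 years. If sites comply, last contact and last PSA nearly coincide and the rule does no harm. That stands as far as it goes. But Section 7.10 and footnote 14 relax the requirement for the exposed subjects, so the documents conflict, and the endpoint should not depend on the favourable reading.

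The exposed group is also limited. Subjects who leave for PSA-defined castration resistance or symptomatic deterioration already have an event. That stands too.

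A reader might infer that the 2-year proportion is certain to be overstated. The documents do not support this: phone or email is permitted, not prescribed, and no phone-only share is given.

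A reader might also infer that radium toxicity sends Arm B subjects to phone follow-up and so tilts the comparison. Section 7.10 says otherwise: subjects off radium-223 or bicalutamide for toxicity but still castrated remain on protocol therapy. What the design does imply is more radiographic exits in the control arm. Under the assumed medians of 12 and 19 months, 2-year rPFS is 2^(−24/12) = 25% against 2^(−24/19) = 42%. If those exits became phone-only at equal rates, the control proportion would tend to be inflated more, which works against radium-223. Even that depends on how PSA is collected after therapy.

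Finally, the illustrated bias of 1 to 3 points is smaller than sampling error. Near 33%, an approximate 90% half-width, ignoring censoring, is 1.645 × √(0.33 × 0.67/n), about 9 points for n = 68 and 7 for n = 136. This tempers the importance, but a bias in a known direction is not covered by the interval.

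**Conclusion.** The censoring rule in Section 8.4 is wrong as written. Any time with contact but no PSA is credited as PSA-progression-free, and each arm's 2-year PSA-PFS is then biased upward.

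The size cannot be fixed from the documents. The closed-form range of about 1 to 3 points rests on assumed PSA-PFS rates, assumed shares of 10 to 30% leaving PSA monitoring, exponential times, the 44-month survival figure, and leaving that is unrelated to PSA risk. Heavier loss of PSA monitoring gives more; PSA drawn as footnote 4 requires gives close to none. An effect on the between-arm test, and its direction, is conditional on exposure or PSA risk after leaving differing by arm.

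This concerns a secondary endpoint. The primary rPFS analysis already censors at the last assessment and is unaffected.

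**What to change.** - In Section 8.4, censor subjects without an event at the date of their last PSA assessment, in line with Sections 8.8 and 12.6.
- Keep death and symptomatic deterioration as events, and state how a death after a long gap in PSA is handled. Counting such deaths while censoring survivors at last PSA gave slightly low estimates in the simulation.
- Report last-contact censoring as a sensitivity analysis. Note that censoring at last PSA removes the bias only if leaving PSA monitoring is unrelated to PSA risk, and otherwise reduces it.
- Reconcile calendar footnote 4 and the calendar's follow-up column with footnote 14 and Section 7.10 on whether PSA is required after therapy stops.

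The cost is a few sentences and one extra analysis. There is no change to sample size or the primary test. Where contact has outrun PSA, the reported proportions will be somewhat lower.

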### **8.5 PSA Response Categories**

- Undetectable PSA is defined as a PSA level of  $\leq 0.2$  ng/mL after seven cycles.
- A PSA partial response (PSA PR) after seven cycles is defined as a PSA that is between 0.2 and 4 ng/mL.

### **8.6 Time to Castration Resistance**

Castration resistant prostate cancer is defined as either PSA progression or radiographic progression. Time to Castration resistance will be counted from start of ADT (first LHRH agonist/antagonist/surgical castration) to development of castration resistance by either criterion:

- **PSA progression** per 10.2.1. Castration resistance will be determined to have occurred at the time of the first PSA increase.

- **Radiographic progression** Castration resistance will be determined to have occurred at the time of the first imaging assessment showing progression not the confirmatory scan (for bone lesions).

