### 5.5.3 Continuation of ADT/completion of Radium-223

After the completion of seven cycles of ADT, further treatment with androgen deprivation will be up to the treating physician. If radium-223 dichloride doses have been delayed for any reason and all 6 doses have not been administered by the 28 weeks' time-point, they may be administered later at the discretion of the site investigator provided laboratory parameters as outlined above are satisfied. The site investigator/site should record data on such delayed radium-223 administrations including dose of radium-223 dichloride, date of administration and hematological parameters obtained within 3 days of administration.

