**Footnotes: Please NOTE: unless otherwise specified, all testing will be performed in BOTH arms.**

- NOTE:** Early induction subjects will have initiated ADT prior to registration. Results of screening procedures should be obtained through medical records if available including start date ADT therapy.
- Close monitoring for fractures should be done during the physical exam. If a fracture is suspected, radiological exams should be performed per clinical guidelines. Subjects should be encouraged to contact the site investigator for any new onset pain or increase in pain in sites of known bone disease.
- CBC w/diff and platelet to include: WBC with differential and platelets, hemoglobin and hematocrit. Additional monitoring of CBC w/diff and platelet per site investigator's discretion based on subject clinical status. CMP blood chemistries to include: sodium, potassium, chloride, bicarbonate, blood urea nitrogen (BUN), serum creatinine, glucose, calcium, total protein, albumin, AST, ALT, alkaline phosphatase, total bilirubin. Magnesium and phosphorus to be included.
- PSA, Alk Phos to be assessed Cycle 1 Day 1 (late induction group) or Cycle 2 Day 1 (early induction group). Subjects will be followed for PSA and Alk Phos every month for a total of 1 year from randomization then every 12 weeks (± 14 days) for the next year (2 years from randomization). If a subject withdraws consent, he is deemed "off study" and will NOT be followed further.
- Testosterone (serum) will be measured on Cycle 1 Day 1 (for late induction group only), Cycle 8 Day 1 (both early and late induction groups) and after 12 months of ADT. For early induction subjects, a testosterone value prior to initiation of ADT should be obtained via medical records, if available. If the result is not available, subjects are not ineligible for study.
- AE and concomitant medication assessment: AE assessment should include a review of any symptoms the subject may be experiencing. In addition, the subject should be assessed for secondary malignancies. Concomitant medication review will include all medications the subject is taking.
- Pain assessment with BPI (short form) and assessment of analgesic use with WHO ladder scale will be performed at 3 time-points: Cycle 1 Day 1 (late induction group) or Cycle 2 Day 1 (early induction group), on Cycle 4 Day 1 and Cycle 8 Day 1.

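### Time to castration resistance (8.6) has no castrate-testosterone condition, so a man who stops ADT, recovers testosterone and then progresses counts as castration resistant

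*Combined protocol and SAP*

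**What the plan says.** Section 8.6 is the only definition of the TTCR endpoint: "Castration resistant prostate cancer is defined as either PSA progression or radiographic progression", counted from the start of ADT. For the PSA part it cites 10.2.1. The PSA rule is in fact in 8.2.1, and 10.2 is the bicalutamide drug information. Section 8.2.1 asks for "two consecutive increases in PSA over the nadir PSA, at least two weeks apart AND an absolute increase of at least 2 ng/mL" and is also silent on testosterone.

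Section 7.10 lists the reasons for ending protocol therapy. One is "development of castration-resistant prostate cancer by PSA criteria in conjunction with castration range serum testosterone level ( $< 50$ ng/dL"); another is "radiologic disease progression or symptomatic deterioration despite castration range serum testosterone level ( $< 50$ ng/dL").

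On the duration of ADT, section 5.5.3 says: "After the completion of seven cycles of ADT, further treatment with androgen deprivation will be up to the treating physician". Sections 7.6 and 7.8 say that ADT may go on for up to two years from randomization. Section 5.2 says LHRH therapy is given continuously, but sets no duration.

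The calendar footnotes have PSA followed monthly for one year and then every 12 weeks for a second year, with no condition that ADT is ongoing. On testosterone they say: "Testosterone (serum) will be measured on Cycle 1 Day 1 (for late induction group only), Cycle 8 Day 1" (both induction groups) and after 12 months of ADT. The calendar also marks it at screening. Section 7.3 lists it at cycles 2 to 7, where the calendar does not.

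Section 12.7 reports TTCR by arm with Kaplan-Meier methods and a log-rank test in the ITT population. Neither 8.6 nor 12.7 says what happens when a man comes off ADT.

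**The concern.** Castration resistance means progression while testosterone is at castrate level. A PSA rise after testosterone has recovered may only reflect the withdrawal of ADT. The endpoint as defined cannot tell the two apart, and the protocol permits the circumstances in which they differ.

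TTCR is a named secondary objective, reported by arm and tested between arms. If an appreciable share of its events are non-castrate progressions, the reported medians are shortened and the comparison mixes resistance with treatment withdrawal. No blinding of treatment is described and continuing ADT is a discretionary decision, so stopping rates could differ between arms. Without a testosterone value near progression, the two kinds of event may also be impossible to separate at analysis.

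**Working it through.** **1. The plan's nearest figure.** No event count or power is stated for TTCR. The 140 events in section 12.1 belong to radiographic progression-free survival (rPFS). They reproduce: with HR = 12/19, one-sided alpha 0.10, 90% power and 1:2 allocation, (1.2816 + 1.2816)² / [(1/3)(2/3)(ln 12/19)²] = 140.0. The rPFS event is radiographic progression or death with no reference to castration, so this figure is untouched.

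**2. The texts side by side.**

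| Place | PSA or radiographic rule | Testosterone below 50 ng/dL required? |
|---|---|---|
| 8.6 (TTCR endpoint) | either kind of progression | No |
| 8.2.1 (PSA progression) | two consecutive rises plus 2 ng/mL | No |
| 7.10 (ending therapy, PSA) | the same PSA rule | Yes, in the trigger |
| 7.10 (ending therapy, radiologic) | radiologic progression | Yes |

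The path through 8.6 is then: ADT stopped after cycle 7 (5.5.3), testosterone recovers, PSA still collected (calendar footnotes), 8.2.1 met, TTCR event recorded. No rule in 8.6 or 12.7 interrupts it.

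**3. How much follow-up is exposed.** Seven 28-day cycles end on day 7 × 28 = 196. Of a two-year (730-day) follow-up, (730 − 196)/730 = 73% lies after ADT becomes optional. PSA visits after cycle 7 are C8, C9–12, C13, C14–16 and C17 Day 28, ten in all. Two of them (C8D1 and C13D1) carry a testosterone test. C13D1 is day 12 × 28 + 1 = 337, so none is scheduled for the last (730 − 337)/730 = 54% of the period.

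**4. Illustration of size (all inputs assumed).** Let true TTCR be exponential with median m. A fraction f stops ADT at month 6.4 (196 days), and PSA progression in those men is exponential with a 6-month median, beginning a lag L after stopping. For t beyond 6.4 + L,

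S(t) = exp(−λt) × [(1 − f) + f × exp(−μ(t − 6.4 − L))], with λ = ln 2/m and μ = ln 2/6.

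The reported median solves S(t) = 0.5. For m = 15, f = 0.2, L = 0 and t = 12.7: 0.556 × (0.8 + 0.2 × 0.483) = 0.50.

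| True median | Lag L | f = 10% | 20% | 30% |
|---|---|---|---|---|
| 15 months | 0 | 13.7 | 12.7 | 11.8 |
| 15 months | 3 months | 14.1 | 13.4 | 12.8 |
| 15 months | 6 months | 14.5 | 14.2 | 13.9 |
| 19 months | 0 | 17.0 | 15.2 | 13.8 |

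The lag matters because section 5.2 allows depots of three months to a year, so suppression can outlast cycle 7. At 30% stopping, a six-month lag cuts the loss from 3.2 months (15 − 11.8) to 1.1 (15 − 13.9).

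**The case against.** Section 7.10 is a discontinuation rule, not an endpoint definition. Its testosterone phrase sits in the trigger, and the sentence that then defines castration-resistant disease repeats the PSA rule with no testosterone condition. One can read 7.10 as requiring castrate testosterone for the decision to stop therapy and nothing more. That stands: this is an inconsistency to reconcile, not a clash between two endpoint definitions. It does not rescue 8.6, which still counts non-castrate progression under the name of castration resistance.

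Section 5.2 says ADT is continuous, and orchiectomy, which cannot be stopped, is an allowed method. Nothing suggests that stopping is planned or common. This limits the likely size, but 5.2 sets no duration and does not override the discretion in 5.5.3.

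Three stronger readings are tempting and are not supported:

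- A reader might infer that every man who stops ADT after cycle 7 is counted as castration resistant. Stopping is not an event; he must later meet the PSA or radiographic rule.
- A reader might infer that the comparison between arms is biased. That needs stopping rates that differ by arm, and the documents give none. With similar rates the effect would mainly be dilution.
- A reader might take the mismatch between 7.3 and the calendar as the missing data. It concerns cycles 2 to 7, before ADT becomes optional. The gap that matters here is after C13D1.

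**Conclusion.** The point holds as a defect in the definition of one tested secondary endpoint. That 8.6 omits the castrate condition, and that no rule covers progression off ADT, follows directly from the text and needs no assumption.

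The size does not follow from the text. The shifts shown above, from 0.5 to 3.2 months on a true median of 15, rest on assumed stopping rates, an assumed true median, an assumed time to PSA progression and an assumed lag. They are a range, not an estimate. Neither the direction nor the existence of a bias between arms is established. The rPFS analysis and its 140 events are unaffected.

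**What to change.** 1. In 8.6, count PSA or radiographic progression as a TTCR event only with testosterone below 50 ng/dL at that time, or after orchiectomy, and align the wording with 7.10.
2. State in 8.6 and 12.7 how progression off ADT is handled, for example by censoring at the last assessment on ADT. Stopping is the physician's choice, so such censoring may be informative and departs from full ITT follow-up. Keep the present 8.6 definition as a sensitivity analysis, and report by arm how many men stopped ADT and how many progressed off it.
3. Record a testosterone value at suspected progression. Section 7.10 already needs it for the discontinuation decision, and none is scheduled after C13D1.
4. Reconcile 7.3 with the calendar on testosterone at cycles 2 to 7, and correct the cross-reference in 8.6 from 10.2.1 to 8.2.1.

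The cost is wording, a few more testosterone values to record, and somewhat fewer TTCR events.

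### Time to castration resistance (8.6) omits the testosterone < 50 ng/dL condition of 7.10, although ADT may stop after cycle 7, so a PSA rise on testosterone recovery would count as an event

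*Combined protocol and SAP*

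**What the plan says.** Section 8.6 defines the event: "Castration resistant prostate cancer is defined as either PSA progression or radiographic progression". For the PSA route it adds the date: "Castration resistance will be determined to have occurred at the time of the first PSA increase". It cites 10.2.1 for PSA progression. Section 10.2 is the bicalutamide drug information, so 8.2.1 must be meant. There the event "is defined by two consecutive increases in PSA over the nadir PSA, at least two weeks apart AND an absolute increase"; the minimum size set for that increase is 2 ng/mL. Neither 8.6 nor 8.2.1 to 8.2.3 mentions testosterone.

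Section 7.10 does mention it, with a threshold of 50 ng/dL, in its list of reasons for stopping protocol therapy. The PSA reason reads: "If there is development of castration-resistant prostate cancer by PSA criteria in conjunction with castration range serum testosterone level". The imaging reason has the same threshold and reads: "If there is evidence of radiologic disease progression or symptomatic deterioration despite castration range serum testosterone level".

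On ADT, 5.5.3 says: "After the completion of seven cycles of ADT, further treatment with androgen deprivation will be up to the treating physician". Sections 7.6 and 7.8 say only that it may continue, up to 2 years from randomization. Calendar footnote 5 puts the later testosterone samples at "Cycle 8 Day 1 (both early and late induction groups) and after 12 months of ADT". For PSA, footnote 4 says: "Subjects will be followed for PSA and Alk Phos every month for a total of 1 year from randomization". In the second year the PSA interval is 12 weeks.

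Median TTCR is part of secondary objective 2.2.2. Section 12.7 compares the arms by log-rank test in the ITT population.

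**The concern.** Castration resistance means progression while testosterone is suppressed. Section 7.10 uses the term that way, but the endpoint section does not. Once ADT is optional, a PSA rise can simply reflect returning testosterone. Section 8.6 would score that rise as an event.

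Within an arm the present wording can only add events, so it can only shorten the estimated TTCR. If men stop ADT equally often in both arms, a true difference shrinks and a null result stays at a hazard ratio of 1. If they stop unequally, the ratio can move either way. Unequal stopping is plausible: Arm A receives no placebo infusion (5.1), so the physician who decides on ADT knows the arm, and can also know the 7-month PSA.

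**Working it through.** **1. Schedule.** Counting days elapsed from C1D1, C8D1 is day 7 × 28 = 196 (6.44 months), C13D1 is day 12 × 28 = 336, C14D1 is day 336 + 84 = 420, and C17D28 is day 336 + 4 × 84 + 27 = 699. Scheduled PSA draws after C8D1 are C9–C12 (4), C13 (1), C14–C16 (3) and C17D28 (1), nine in all. Testosterone is scheduled at one of them, C13D1. None is scheduled at the last four draws (days 420 to 699) or at the end-of-treatment visit. Section 7.3 lists testosterone at cycles 2–7, but that precedes the period at issue. C8D1 closes the seven cycles, so it cannot show recovery after a stop at that point.

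**2. The plan's own figure.** None is given for TTCR. The rPFS event count reproduces: (1.2816 + 1.2816)² / [(2/9) × ln(12/19)²] = 140. Nothing here changes it.

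**3. Scenario inputs.** The documents give no ADT stopping rate and no TTCR median, so these are assumptions:
- TTCR medians of 12 v 19 months (the rPFS medians as stand-ins); hazards l = ln2/12 and ln2/19; ratio 0.632.
- Dropout 10% a year: g = −ln(0.9)/12 per month; 68 and 136 men.
- A share p of men still event-free at 6.44 months stop ADT then and recover testosterone; median 6 months from stop to a PSA event, m = ln2/6.

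Men at risk at 6.44 months: 68 × exp[−(ln2/12 + g) × 6.44] = 44.3 and 136 × exp[−(ln2/19 + g) × 6.44] = 101.6.

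**4. Current 8.6 rule.** For t > 6.44, S(t) = exp(−l·t) × [(1 − p) + p·exp(−m(t − 6.44))]. Solve S = 0.5 for the median. Check for Arm A at p = 20%, t = 10.62: 0.5415 × (0.8 + 0.2 × 0.617) = 0.500. The hazard ratio is the root of the expected Cox score over 24 months.

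| p, both arms | Medians A v B (months) | Difference | HR | Non-castrate events by month 24 |
|---|---|---|---|---|
| 0 | 12.0 v 19.0 | 7.0 | 0.632 | 0 |
| 10% | 11.2 v 17.0 | 5.8 | 0.652 | 9.6 |
| 20% | 10.6 v 15.3 | 4.6 | 0.672 | 19.1 |
| 30% | 10.1 v 13.8 | 3.7 | 0.691 | 28.7 |

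At p = 20%, changing the lag median to 3 or 12 months gives differences of 4.1 or 5.3 months and 23.7 or 13.2 such events.

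Unequal stopping, lag 6 months: 10% in A and 30% in B gives 0.78; the reverse gives 0.58. With no true effect (12 v 12) the same splits give 1.13 and 0.89.

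**5. Depot carry-over.** Section 5.2 allows depots of up to one year, so castration can outlast C8D1. Delaying the first excess event by 3 months at p = 20% gives 11.3 v 15.9 months and HR 0.665. A 6-month delay leaves the Arm A median at 12.0 and gives HR 0.658; the 10%/30% null ratio falls to 1.075.

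**6. Testosterone condition with non-castrate men kept at risk.** If stoppers stay non-castrate to month 24, S(t) = (1 − p)·exp(−l·t) + p·exp(−l × 6.44). At p = 20% in both arms the medians become 13.7 v 23.3, a difference of 9.6 months, with HR 0.647. With no true effect, 10% in A and 30% in B gives 0.84; the reverse gives about 1.20. These null ratios lie further from 1 than those in step 4.

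**The case against.** Four points deserve weight.

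- **The condition is already in the protocol.** The PSA bullet in 7.10 both defines castration resistance and requires castrate testosterone, so a careful analyst could harmonise the sections, and a site applying 7.10 needs a value at progression. This stands in part. But 8.6 is the endpoint definition, it does not refer to 7.10, and it cites a section that does not contain the criterion.
- **Other data can identify these men.** A reader might infer that, with testosterone so sparse, the cases cannot be sorted out afterwards. That is too strong: concomitant medications are reviewed at every scheduled visit, including C9–C12 and C14–C17, and would show many of the ADT stops. They do not confirm castrate status after LHRH therapy has stopped, because depot cover and recovery time vary.
- **The size rests on assumed inputs.** This stands. Section 5.2 calls for continuous LHRH therapy, which may keep stopping rare, and carry-over reduces the effect.
- **A testosterone condition alone can do harm.** This stands, and it shapes the fix. When stopping is unequal, keeping men at risk who cannot have the event biases the ratio the opposite way, and can create an apparent radium benefit (null ratio 0.84).

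**Conclusion.** The defect is real: 8.6 as written counts progression in non-castrate men as castration resistance, against the meaning used in 7.10. It affects one secondary endpoint and should be corrected.

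Its size is unknown. With equal stopping of 10% to 30% the ratio moves from 0.632 to about 0.65–0.69, less with depot cover. Stopping split 10%/30% between the arms moves a null ratio to about 0.89 or 1.13. At p near 0 nothing changes. All of this assumes rPFS medians as stand-ins, stops at 6.44 months and exponential times.

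Two stronger inferences are not supported. One is that the trial's main result is at risk: rPFS (8.8) counts radiographic progression or death without using the term castration resistance, and its test and 140-event target do not depend on 8.6. The other is that TTCR is biased in a known direction between arms: no document says how often, or in which arm, ADT would stop.

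**What to change.** In 8.6:

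- Require serum testosterone < 50 ng/dL for castration resistance: on the PSA route at the confirming PSA, from the same blood draw where possible; on the radiographic route within a stated window of the progressing scan (28 days, for example). Keep the present dating at the first PSA increase.
- If testosterone is missing, accept orchiectomy or documented LHRH therapy in effect; otherwise do not count the event. A rise with testosterone ≥ 50 ng/dL is not an event.
- Correct the cross-reference from 10.2.1 to 8.2.1.

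In 12.7:

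- Do not rely on keeping non-castrate men at risk. Also report TTCR with men censored at loss of castration (documented ADT stop or testosterone ≥ 50 ng/dL), and say in advance which of the two analyses leads.
- Report the current 8.6 definition as a sensitivity analysis.
- Show the proportion off ADT by arm, for example at C13D1 and C17D28.

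Leave rPFS, PSA progression-free survival (8.4) and the primary test as they are.

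The cost is some wording, one extra assay at progression and two further TTCR analyses. Some testosterone values will be missing, because footnote 13 lets later follow-up come from local records. Censoring at the ADT stop may be informative if physicians stop in men who are doing well, which is why no single version should stand alone.
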